6.6 SAFETY FOLLOW-UP

On Day 1 following each infusion, the participant will be evaluated by study staff to assess for any infusion related adverse reactions or complications. This assessment can be done in person, over

the phone, by email or a teleconference. At 7-10 days post each infusion, a member of the study team will contact the parent or guardian via phone, teleconference, or email to assess patient status and any adverse events. A questionnaire (see Appendix 1) will be administered at each subsequent visit and at 3, 9 and 12 months to assess for serious adverse events. PRA will be obtained pre-treatment and at 6 and 12 months after the initial infusion.

7.0 STUDY PLAN

7.1 OVERVIEW

Parents/Guardians who have previously contacted our program and have a child who may meet eligibility criteria for this study will be notified that this study is available. After initial contact, parents/guardians of potential research participants will have an initial phone or teleconference interview with study personnel to describe the study, verify basic eligibility criteria, and confirm their interest in participation. The participant's eligibility will then be screened through review of medical and psychological records, therapy records, video, photos, cognitive and diagnostic testing, and laboratory testing under a separate screening protocol and consent.

Once all screening is complete and the participant is likely to meet study criteria, the participant will travel to Duke for their first visit. During their baseline visit at the Duke Center for Autism and Brain Development, the informed consent will be obtained and participant eligibility will be determined by physical observation and verification of ASD diagnosis per BOSA and DSM-5 criteria. During his/her first visit, he/she will also undergo additional clinical and observational evaluations, and SenseToKnow app assessments. Participants will be evaluated the day after infusion either in person, via teleconference, or by phone call and parents will be contacted 7-10 days after infusion for follow up safety evaluation. Participants will return to Duke six months later for repeated clinical and observational evaluations, and SenseToKnow app assessments, and safety follow-up. At 12 months post-infusion, remote safety assessment and parent-completed behavioral questionnaires will be completed.

7.2 PARTICIPANT SCREENING

Screening for the study is conducted under a separate, IRB-approved screening protocol (Pro00063563). Under this protocol, after written informed consent is obtained from a parent/guardian, the participant's medical and psychological records, therapy records, photographs, behavioral videos, and results of all genetic testing are obtained and reviewed by two teams. The medical review is conducted by a team of pediatric nurses, nurse practitioners, and physicians to identify the presence of any metabolic, immunologic, neurologic, sensory, genetic, or laboratory exclusion criteria. If no such exclusion criteria are identified, the psychiatric review is then conducted by a combination of psychologists, psychiatrists, and other clinically trained staff with expertise in diagnosing and treating children with ASD. They perform an extensive review of the participant's psychological records as well as any therapy records available. A participant must be approved by both medical and psychiatric screening teams to proceed with further laboratory or phone, teleconference, or in-person screening and study enrollment. Should a concern for a previously undiagnosed condition or genetic finding arise during the screening process, this will be discussed with the participant's parent(s)/guardian(s) and a referral will be made to an appropriate medical or psychiatric provider for evaluation and treatment, if indicated.

7.3 STUDY INFUSIONS

All participants will receive an infusion of allogeneic hCT-MSC cells. On the day of infusion, hCT-MSC cells will be thawed and prepared by the CT2 GMP laboratory and/or Duke Stem Cell Lab

per standard operating procedure and provided for infusion of the participant in the clinic under the supervision of the study team and Pediatric Blood and Marrow Transplant Program staff. Baseline vital signs (heart rate, blood pressure, temperature, respiratory rate) will be obtained. A peripheral IV will be placed by clinical staff, anesthesia or a member of the study team. Prior to the infusion, premedications (Benadryl, Solumedrol) will be administered. The study product will be infused over 30-60 minutes. The child will be observed in the clinic for a minimum of 30 minutes after the infusion. IV fluids (D5 ½ NS) at 1.5 maintenance will be attempted. Participants will be discharged from clinic after at least 1 hour providing all vital signs are at their baseline and they are asymptomatic with no evidence of toxicity. Participants will be evaluated by study staff the day after the infusion to assess for any infusion-related adverse reactions or complications. A phone call to parents/guardians by study staff to assess safety of the infusion will be conducted 7-10 days after the infusion.

If a participant has evidence of illness on the day of planned infusion, including but not limited to fever >38.5° C, vomiting, diarrhea, or respiratory distress, the infusion will be postponed.

7.4 CARE DURING UNEXPECTED EVENTS

In the event that a participant develops signs or symptoms of anaphylaxis including urticaria, difficulty breathing, cough, wheezing, or vomiting during his/her study infusion, the infusion will be interrupted and appropriate medical therapy initiated.

7.5 ASSESSMENTS

The following child assessments will be conducted at the Duke Center for Autism and Brain Development according to the schedule outlined in section 7.6:

Respondent	Measure	Domain	Length of Administration
	Brief Observation of Symptoms of Autism (BOSA)*	ASD Diagnosis	45-60 minutes
Clinical Assessments	Developmental Assessment of Young Children, Second Addition (DAYC-2) *	Cognitive/Language	45-60 minutes
	Clinical Global Impressions Scale – S and I	Autism symptoms	10 minutes
	JERI rating based on Parent-Child Interaction Task (PCIT)	Social communication	12 minutes
Biomarker Assessments			
Diomarker Assessments	SenseToKnow (S2K) Application with Computer Vision Analysis (CVA)	Autism symptoms	10 minutes

*The DAYC-2 and BOSA are only conducted during screening

7.5.1 Assessments for Diagnosis of Autism Spectrum Disorder:

Diagnosis of ASD will be confirmed by the DSM-5 Checklist, which will be informed by the Brief Observation of Symptoms of Autism (BOSA) Assessment. Clinical research staff that have been certified as research reliable in the administration of the ADOS-2 will complete diagnostic evaluations.

Brief Observation of Symptoms of Autism (BOSA): This assessment will be used to help inform a DSM-5 diagnosis of ASD. The BOSA is a semi-structured parent-child interaction that lasts between 12 to 16 minutes. Age and verbal ability are used to determine the appropriate module of the BOSA. A clinician who is research-reliable on the ADOS-2 observes the BOSA and scores a corresponding ADOS-2 protocol. Following completion of the BOSA, an algorithm is used to map these binary codes onto a DSM checklist. The BOSA is only completed at the baseline visit.

Diagnostic Statistical Manual-5 Checklist (DSM-5): This is a clinician checklist based off of diagnostic criteria for ASD within the Diagnostic and Statistical Manual of Mental Disorders, Fifth Edition. Diagnostic criteria are taken from the DSM-5, and are utilized in order to confirm appropriate ASD diagnosis for inclusion in the study. This checklist is completed by trained clinicians using the clinician's best judgment and is informed by information gathered during the administration of the BOSA. The DSM-5 Checklist takes about 3-5 minutes to complete. This checklist is completed at baseline.

7.5.2 Other Clinician Assessments:

Developmental Assessment of Young Children- Second Addition (DAYC-2): ⁹² The Developmental Assessment of Young Children (DAYC-2) is a cognitive based assessment designed to identify delays in very young children and preschoolers from birth through 5 years. Only the Cognitive scale will be administered. Test administration time varies from 10-20 minutes per domain. This assessment will be conducted during the baseline visit only.

SenseToKnow (S2K) Application (app): The application consists of a series of brief dynamic stimuli (including short, <1 minute movies and games) which are designed to elicit early risk behaviors related to autism. The application records the child's behavior via the front-facing camera as he or she interacts with the stimuli. Algorithms based on computer vision and machine learning are employed to quantify a multitude of autism symptom behaviors, including attentional responses, preferential gaze, facial affect, and motor responses. [name] and [name] have conducted studies in in-clinic and at-home environments demonstrating that CVA can objectively and reliably quantify autism symptoms.⁹³⁻⁹⁷ The application takes about 10 minutes will be conducted at the baseline and 6 month visits.

JERI Rating based on Parent-Child Interaction Task (PCIT): During a 12-minute Parent-Child Interaction Task (PCIT), the participant will be observed during two contiguous sessions conducted in the same room comprised of (1) a six-minute interactive play session in which the parent joins the child in play and (2) a six-minute independent play session with toys available during which the caregiver will be sitting in the corner of the room completing a questionnaire. The Parent-Child Interaction Task will be completed at the baseline and 6 month visits. Behavior will be video recorded with audio recording. Behavior will then be characterized through two methods: 1) automated video tracking with computer vision analysis, and 2) behavioral coding of child social communication abilities during interactive play using the Joint Engagement Rating Inventory (JERI).⁹¹ Videotapes will be coded using JERI by trained and reliable raters. Computer vision analysis software will be used to automatically track the child's movements and the parent's movements. The purpose of the video tracking is to automatically measure social approach or avoidance and exploration. The primary dependent variable is the time spent in each core region (center of room, periphery of room, near parent, activity table). Exploratory dependent variables will be related to latency, frequency, velocity and movement.

The JERI will be used to code for child engagement states during the first 6-minute parent-child interactive play session. Behaviors that will be rated include: unengaged, object engaged, supported joint engagement, coordinated joint engagement, symbol-infused joint engagement, and total joint engagement. All items are rated on a 1 to 7 scale and factor in both the quantity and quality of each behavioral state of engagement. Dependent variables will include total joint engagement (primary endpoint) and ratings on all items (secondary endpoints).

Vineland Adaptive Behavior Scales, Third Edition (VABS-3) Survey Interview Form:⁹⁸ This will be used to assess social, communication, motor, and adaptive behavior. The assessment is administered to the parent/caregiver using a semi-structured interview format. This assessment

takes about 60-120 minutes to administer. The VABS-3 is a well-standardized measure of several domains of adaptive functioning including socialization, communication, daily living, and motor skills. Norms are available from birth to 90 years. The Socialization subdomain assesses play, interpersonal relationships and coping skills. The Communication subdomain assesses receptive, expressive and written language skills. The Daily Living Skills subdomain assesses personal, domestic and community living skills. The Motor Skills subdomain assesses gross and fine motor skills. The VABS-3 will be completed at the baseline, 6, and 12 months.

Clinical Global Impression (CGI): The CGI is a commonly used rating scale with two components that measures symptom severity and treatment response.

The Clinical Global Impression – Severity Scale (CGI-S) is a 7-point scale that requires the clinician to rate the severity of the participant's symptoms based on parent interview and child observation at the baseline and 6 month visits. The CGI-S requires the clinician to rate the severity of the participant's symptoms of ASD at the time of the assessment, relative to the clinician's past experience with participants who have the same diagnosis. There will be three separate CGI-S ratings; these include social communicative functioning, restricted/repetitive interests and behaviors, and overall. The CGI-S will be completed at the baseline and 6 months.

The Clinical Global Impression – Improvement (CGI-I) is a 7-point scale that requires the clinician to assess how much the participant has improved or worsened relative to baseline based on parent interview and child observation. There will be three separate CGI-I ratings; social communicative functioning, restricted/repetitive interests and behaviors, and overall improvement. The CGI-I will be completed at the 6-month visit.

7.5.3 Parent Caregiver Questionnaires:

All caregiver questionnaires will be completed online through a Duke approved EDC system or by paper. The EDC survey tool is available for Duke users through a university-wide site license. The EDC is integrated with Duke's NetID authentication system but allows sharing of surveys with non-Duke users.

Pervasive Developmental Disorder Behavior Inventory (PDDBI):⁹⁹ The PDDBI was developed to assess responsiveness to intervention in children with ASD. The PDDBI is an informant-based rating scale that is designed for children 1 year, 6 months to 12 years, 5 months. It assesses problem behaviors as well as appropriate social, language, and learning/memory skills. The PDDBI assesses both social impairments typically associated with the active but odd subtype of ASD and development of pro-social skills that are integral to improved reciprocal social behavior. The PDDBI renders raw scores as well as t-scores based on comparisons to a standardized ASD population. The PDDBI has been validated in a PDDBI development sample of 311 children between the ages of 1 and 17 years old. This is a parent questionnaire with 188 items that takes approximately 30-45 minutes to complete. The PDDBI will be administered every three months.

Intervention History Questionnaire: This questionnaire is completed by a primary caregiver to obtain detailed information on behavioral health interventions that the child/family has been involved in over the past 3 months or since the questionnaire was last administered. Information is collected about the type and quantity of interventions, services, and treatments the child is receiving. This questionnaire will be administered at baseline, 3 months and 6 months.

MacArthur-Bates Communicative Development Inventories, Second Edition (CDIs):¹⁰⁰ The CDIs are standardized caregiver-completed report measures which capture information about children's developing abilities in early language, including gestures, production, vocabulary,

comprehension, and grammar. It was developed for use in infants and toddlers ages 8 to 30 months but it may also be used with older children with developmental delays. Because language changes so dramatically during that time span, there are three separate forms for different age ranges and language abilities. Each form generally takes 20-40 minutes to complete.

CDI: Words and Sentences form is designed for children ages 16 to 30 months. This form yields scores for vocabulary production and a number of aspects of grammatical development, including sentence complexity and the mean length of the child's longest utterances. The CDI words and sentences version will be used for all participants. This form will be collected at baseline, 3 months, 6 and 12 months.

Pediatric Quality of Life (PedsQL) 4.0 Generic Core Scales: The PedsQL 4.0 Generic Core Scales is a 5-minute parent questionnaire that measures the child's functioning in the dimensions of: physical, emotion, social and school. The Toddler Parent Report version is composed of 21 items and will be completed at the baseline and 6 month visits and remotely at 12 months.

Center for Autism and Brain Development (CABD) Demographics Form: The CABD demographics form collects race and ethnicity according to the NIH reporting standards. Additional questions collect data to help characterize the population. This parent questionnaire takes less than 10 minutes to complete and will only be completed at the baseline visit.

Medical and Behavioral History Questionnaire (MBHQ): The MBHQ is a broad assessment of medical and behavioral issues. It is completed at baseline, three, six, nine and 12 months.

COVID-19 Exposure and Family Impact Survey (CEFIS): ¹⁰¹ The CEFIS is an open-source parent report questionnaire that conceptualizes exposure to potentially traumatic aspects of COVID-19 and assesses the impact of the pandemic on the family. The CEFIS will be completed every three months. Data collected with the CEFIS measure will be de-identified and shared with the tool developers through a CSV file sent securely using DukeBOX.

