2.8 STUDY DESIGN

This is a single site, prospective study of one intravenous infusion of human umbilical cord tissuederived mesenchymal stromal cells (hCT-MSC) in toddlers with autism spectrum disorder (ASD). Toddlers 18 months to <4 years (3 years 364 days) of age with a confirmed diagnosis of ASD will be eligible to participate. Diagnosis will be confirmed at the time of the eligibility visit at the Duke Center for Autism and Brain Development. All participants will receive a single intravenous dose of 2x10⁶/kg hCT-MSC per kilogram at baseline. Assessments will be conducted at baseline and 6 months, with remote follow-up assessments at 12 months.

The primary purpose of this study is to evaluate safety and feasibility. Safety assessments include monitoring of acute infusion reactions, adverse events, incidence of infections, and markers of alloimmunization. Clinical outcome measures will also be described. A key clinical outcome measure is the change in social communication abilities from baseline to 6 months based on the Joint Engagement Rating Inventory (JERI), a commonly-used and well-validated coding system for rating the quality and quantity of social communication skills in toddlers with and without ASD.⁹¹ JERI coding rates social communication abilities on a 1 to 7 scale and factors in both the quantity and quality of skills. The total joint engagement score as well as ratings on all JERI subscales that comprise the total score will be described.

Other clinical endpoints will include the PDD Behavior Inventory (PDDBI) autism composite score, the mean of the Socialization Subscale Standard Score and Communication Subscale Standard Score on the Vineland Adaptive Behavior Scales (VABS-3), the Clinical Global Impression Scale (CGI) – Severity and Improvement Scales, the Communicative Development Inventories (CDI-2): Words & Sentences subscales, and the Pediatric Quality of Life Scale (PedsQL Generic Core Scale).

Exploratory clinical endpoints will include autism symptoms measured by an app that elicits and records autism symptoms on an iPad (SenseToKnow), PDD Behavior Inventory (PDDBI) Subscales, and VABS-3 Standard Score and age equivalent for the following subscales: Socialization, Communication, and Daily Living and the Standard Score and age equivalent for the VABS-3 Adaptive Behavior Composite.

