4.0 STUDY DESIGN

4.1 GENERAL DESIGN

This is a single site, phase I, open-label, prospective study of one intravenous infusion of human umbilical cord tissue-derived mesenchymal stromal cells (hCT-MSC) in 12 toddlers \geq 18 months to <4 years (3 years 364 days) of age with autism spectrum disorder (ASD). All participants will receive a single intravenous dose of 2x10⁶ hCT-MSC per kilogram at baseline. The primary outcome is safety, as measured by the incidences of infusion reactions, infections, and new-onset clinically significant anti-HLA antibodies. The main clinical outcome measure is the change in social communication abilities from baseline to 6 months based on the Joint Engagement Rating Inventory (JERI).⁹¹ Duration of study will be 12 months from the time of the initial infusion.

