8.0 STATISTICAL CONSIDERATIONS

8.1 STUDY DESIGN

This is a single site, Phase I, prospective study of intravenous hCT-MSC infusion in 12 children 18 months to <4 years (3 years 364 days) of age with ASD. All participants will be treated with hCT-MSC. Participants will receive a single hCT-MSC infusion at baseline and evaluated at 6 (in person) and 12 (remotely) months post-infusion. Duration of study participation will be 12 months from the time of the first infusion.

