8.4 SAMPLE SIZE AND POWER CALCULATIONS

The proposed trial is an open label Phase I trial of one intravenous infusion of hCT-MSC in toddlers 18 months to <4 years (3 years 364 days) of age with a diagnosis of ASD. The primary outcome is safety, as measured by the incidences of infusion reactions, infections, and new-onset clinically significant anti-HLA antibodies. Efficacy measures will also be assessed. The primary efficacy measure is coded time spent in sustained engagement with the caregiver in a brief semi-structured parent child interaction task (PCIT). The change on this outcome measure from Baseline to Month 6 will be analyzed.

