11.2 VIDEO AND AUDIO RECORDINGS

Video recordings of potential participants from parents and guardians may be submitted and used for determining study eligibility. Audio and video recordings may also be obtained of portions of the evaluations and interviews if indicated with parental consent, and may include full facial features and audio. The recordings will be used solely for analysis by the research team or for educational purposes if consent is obtained from the parent/guardian. They will be stored electronically on a password-protected server and identified by the participants' study ID. Software used to conduct and record visit assessments completed remotely will be done on Duke approved platforms and participants will receive instructions to enhance privacy and security measures.

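### Section 8.4 names a different primary efficacy measure from 4.3, 7.5.2 and 8.6, and 7.5.2 does not require the JERI coders to be masked to visit

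*Combined protocol and SAP*

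**What the plan says.** **Design.** Section 4.1: "This is a single site, phase I, open-label, prospective study". Section 8.1: "All participants will be treated with hCT-MSC". Sections 4.1, 8.4 and 8.5 make safety the primary outcome. Section 4.1 makes JERI change at 6 months the main clinical outcome, and objective 2 in 3.0 rests on the same construct.

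**Coding.** Under 7.5.2 the parent-child task is run at baseline and 6 months: "Behavior will be video recorded with audio recording". On the coders: "Videotapes will be coded using JERI by trained and reliable raters". JERI is applied to the first six-minute session. Six behaviors are rated, total joint engagement being one of them: "All items are rated on a 1 to 7 scale and factor in both the quantity and quality of each behavioral state of engagement". Section 11.2 says of the recordings: "They will be stored electronically on a password-protected server and identified by the participants' study ID".

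**Which measure.** Sections 4.3 and 8.6 give a JERI total score with range 1-7. Section 7.5.2 labels total joint engagement the primary endpoint among the JERI variables. Section 2.8 says: "The total joint engagement score as well as ratings on all JERI subscales that comprise the total score will be described". Section 8.4 says: "The primary efficacy measure is coded time spent in sustained engagement with the caregiver", and adds that the change in that measure to Month 6 is what will be analyzed.

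**The concern.** A duration and a 1-7 rating are different variables, with different units and coding rules. While 8.4 disagrees with the endpoint sections, the plan does not fix which one carries objective 2, and the choice could be made after the data are seen.

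On coding, the task is filmed once before and once after the infusion, so a coder who knows the visit knows the treatment status. The rating includes a judgement of quality. Reliability means that raters agree with each other; it gives no protection against an expectation they share. Section 2.7 calls these ratings objective, but no masking procedure supports that word. Most of the other listed clinical measures come from parents, or from clinicians using parent interview, and those people know the child was treated. JERI is scored from recordings, so it is the human-rated outcome that is easiest to mask.

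**Working it through.** **1. The measure, section by section**

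| Section | Measure named | Form |
|---|---|---|
| 4.3, 8.6 | JERI total score | 1-7 |
| 7.5.2 | total joint engagement, one of six rated items | 1-7 |
| 2.8 | total joint engagement score, and subscales said to make up the total | 1-7 scale |
| 8.4 | time in sustained engagement | duration |

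The duration is in none of the lists in 4.3 or 8.6. Section 7.5.2 gives no procedure for it: the only time-spent variable there is time in each region of the room, taken from automated tracking. If the duration were coded from the first session, it would run from 0 to 6 x 60 = 360 seconds. That session is an inference. Section 8.4 does not say which part of the 12-minute task it means, but in the second session the caregiver sits apart.

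There is a smaller ambiguity in the rating itself. Section 2.8 describes a total made up of subscales, while 7.5.2 lists total joint engagement as a single item. Six items rated 1-7 would sum to between 6 and 42, so a total that runs 1-7 cannot be their sum. It fits the single item (or a mean, which no section mentions).

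**2. Masking**

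The supplied text has no requirement on masking coders to visit, on clip order, on when coding is done, or on whether coders may also attend visits. The only masking mentioned is face masking for COVID-19 in 2.9. Labelling by study ID in 11.2 does not address visit. Coding clips unmasked and in visit order would therefore follow the plan. Two measures do not depend on a human rater, the automated tracking and the SenseToKnow app, but neither rates joint engagement.

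**3. Size, for illustration only**

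The plan gives no SD, interval, test or success rule for JERI, so there is no figure to reproduce. From the plan: n = 12 and a 1-7 scale. Assumed: k children are rated one whole point too high at 6 months from expectation alone; SD of change is 0.8, 1.0 or 1.5; a 95% t-interval is reported.

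- Shift in mean change = k/12: 1/12 = 0.08, 3/12 = 0.25, 6/12 = 0.50 points.
- Half-width without bias = t(0.975, 11 df) x SD / sqrt(12) = 2.201 x SD / 3.464 = 0.635 x SD: 0.51, 0.64 and 0.95 points.
- Coverage of the change an unbiased rater would record, by simulation (200,000 trials per cell; normal unbiased changes, +1 added to k of 12):

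| SD of change | k = 1 | k = 3 | k = 6 |
|---|---|---|---|
| 0.8 | 95% | 89% | 64% |
| 1.0 | 95% | 91% | 73% |
| 1.5 | 95% | 93% | 84% |

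The simulation treats unbiased changes as continuous. Rounding them to whole points moves the lowest cell from 64% to about 68%.

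**The case against.** The strongest reply is that silence does not mean unmasked coding. A coding manual or operating procedure may already require masking. That stands: a reader might infer that the raters will be unmasked, or that JERI results will be inflated, and the documents show neither. They show only that a safeguard is not written down. An upward direction is plausible, but no section supports it.

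Second, the consequence is limited. Safety is primary, JERI scores are to be described, and no decision rule depends on them. In 12 toddlers without a control group, maturation and concurrent therapy would confound any change even with perfect masking. This also stands and bears on priority. It does not remove the point, because a described mean is shifted by rater bias just as a tested one is.

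Third, recordings are stored, so masked re-coding stays possible. True, but the plan does not provide for it, and it would mean coding the footage twice.

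Fourth, it is tempting to say that 4.3, 7.5.2 and 8.6 agree exactly and 8.4 alone is out of line. They agree on a 1-7 JERI rating, but only 7.5.2 identifies the item as the endpoint, so correcting 8.4 alone would leave the total score undefined.

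**Conclusion.** The two parts carry different weight. The conflict over the measure is an error on the face of the text: 8.4 cannot stand beside 4.3, 7.5.2 and 8.6, and those three sections favor a 1-7 rating. Nothing suggests that the mismatch was deliberate.

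The masking part is a recommended improvement, not a demonstrated error. The plan allows unmasked coding of a judgement-based rating where visit reveals treatment status. Under the stated assumptions the effect runs from negligible (one child, coverage still 95%) to large (six children, coverage 64% to 84%), and the documents give no basis for choosing a value. Two further readings go too far. The safety conclusions are not touched. Masking would reduce the bias but not remove it, since children look older at 6 months and the audio may give cues, and it would not make the change attributable to the infusion.

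The finding rests on the supplied text. Part of the background in 2.6 was not available, but that is an unlikely place for a coding rule. Both changes should be made; neither bears on the primary outcome.

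**What to change.** **Section 8.4.** Replace the duration with: *the JERI total joint engagement rating (1-7), coded from the six-minute interactive play session of the PCIT*. Use the same name in 2.8, 4.3 and 8.6, so that the total score is explicitly that item.

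**Section 7.5.2.** Add: *Baseline and 6-month videos will be stripped of dates and visit labels and coded in random order, after the last 6-month visit, by trained and reliable raters who did not attend the study visits and are masked to visit.* The condition on attendance is needed because removing labels does not mask someone who was in the room. If a coding manual already says this, cite it.

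**Cost.** The measure needs a wording change in four sections. Masking means relabelling and shuffling up to 12 x 2 = 24 clips of 6 minutes, or 144 minutes of footage (coding time will differ). Coding unmasked and re-coding masked later would mean 288 minutes of footage. JERI results would come only after the last 6-month visit, and the coders must be trained raters not used at visits. Visits and clinical management do not change.
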